5.1.3.3 Dose-Limiting Toxicities

DLTs will be used to determine dose escalation and de-escalation as well as determination of MTD. A DLT is any Grade ≥ 3 non-hematologic AE or any Grade ≥ 4 hematologic AE according to the National Cancer Institute – Common Terminology Criteria for AEs (NCI-CTCAE) version 4.03, occurring during the DLT observation period (Cycle 1) that is judged not to be related to the underlying disease or any previous or concomitant medication. DLTs, along with other safety information (including AEs assessed as not related to the underlying disease or other concomitant medications), will also be used to determine RP2D for M8891 as single agent (Part 1) and the RDE/MTD for M8891 combined with 60 mg of cabozantinib QD (Part 2A).

- DLTs are defined as any of the following pre-defined set of AEs observed in the first treatment cycle for Part 1 (21 days) and Part 2A (22 days; 21 days of M8891 combined with cabozantinib, preceded by 1 day of M8891 single agent) based on predefined set of AEs and judged to be M8891 (or M8891 combined with cabozantinib) related or clinically relevant, (excluding events to be related to underlying disease, medical history or concomitant medications/ procedures in the opinion of the SMC).
- Any death not clearly due to the underlying disease or extraneous causes
- A treatment-emergent AE (TEAE) attributable to study drug that in the opinion of the SMC is of potential clinical significance such that further dose escalation would expose subjects to unacceptable risk
- Evidence of treatment related hepatocellular injury, e.g. alanine aminotransferase or aspartate aminotransferase (ALT/AST) $> 3 \times$ upper limit of normal (ULN) with elevation of serum total bilirubin to $> 2 \times$ ULN, without initial findings of cholestasis (elevated serum alkaline phosphatase) or other apparent clinical causality, including liver metastasis
- Any Grade 4 liver enzyme elevation that is possibly drug related should be considered a DLT. In case of Grade 3 or 4 values, the subject must be monitored until recovery to \leq Grade 2
- Grade 4 neutropenia lasting > 5 days or Grade ≥ 3 neutropenia with fever (temperature of $> 38.3^{\circ}\text{C}$)
- Grade 4 thrombocytopenia lasting > 5 days or Grade ≥ 3 thrombocytopenia with clinically significant bleeding
- Any treatment interruption > 7 days or $> 30\%$ of total dose in Cycle 1 due to AEs not related to the underlying disease or concomitant medication

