5.1.3.5.2 Cabozantinib

The approved dosage of cabozantinib in mRCC is 60 mg once daily without food until the subject no longer experiences clinical benefit or experiences unacceptable toxicity. In Part 2A, cabozantinib will be used at the approved 60 mg free-base equivalent (FBE) daily dosage. After completion of the DLT period in Part 2A and in all cycles of Part 2B, the dose of cabozantinib can be adjusted to 40 mg and then 20 mg to manage AEs (Section 6.5.5). Subjects unable to tolerate a daily dose of 20 mg should discontinue study treatment.

The following should be taken into consideration in decisions regarding cabozantinib dose modifications (reductions or interruption):

- As a general approach all AEs should be managed with supportive care at the earliest signs of toxicity (Table 9 and Table 10). Should this be ineffective, dose reductions or interruptions should be considered to prevent worsening of toxicity.
- The assigned dose for cabozantinib is 60 mg QD. Two dose reduction levels of cabozantinib are permitted (Table 9) if appropriate.
- Dose modification criteria for cabozantinib are shown in Table 10. Dose reductions and/or interruptions should be implemented for unacceptable toxicity. Doses may be modified at any time while on study.

- Dose modifications or interruptions may also occur in the setting of lower grade toxicity than defined in Table 10, if the Investigator feels it is in the interest of a subject's safety and will optimize drug tolerability.
- Interruption of cabozantinib treatment for AEs may occur at any time (except from Cycle 1 in Part 2A) per Investigator discretion. If treatment is interrupted due to AEs for more than 6 weeks, cabozantinib should be discontinued.
- Dose interruptions for reason(s) other than AEs (e.g. surgical procedures) can be longer than 6 weeks but require Sponsor approval. The acceptable length of interruption will depend on agreement between Investigator and the Sponsor.

Table 9 Dose Reductions of Cabozantinib

Assigned dose	First Dose Level Reduction	Second Dose Level Reduction
60 mg cabozantinib oral QD	40 mg cabozantinib oral QD	20 mg cabozantinib oral QD

QD: Once daily.

Cabozantinib should be discontinued if a QD dose of 20-mg cabozantinib (minimum dose) is not tolerated.

Table 10 Dose Modifications of Cabozantinib for Treatment Related AEs

CTCAE v. 4.03 Grade	Recommended Guidelines for Management ^a

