1	Add supportive care as indicated. Continue cabozantinib treatment at the current dose level if AE is manageable and tolerable.
2, tolerable and are easily managed)	Continue cabozantinib treatment at the current dose level with supportive care.
2, intolerable and cannot be adequately managed	At the discretion of the Investigator, cabozantinib should be dose reduced or interrupted ^b .
3 (except clinically non-relevant laboratory abnormalities)	Cabozantinib should be interrupted unless the toxicity can be easily managed with a dose reduction and optimal medical care ^b .
Grade 4 AEs (except clinically non-relevant laboratory abnormalities)	Subjects should have cabozantinib interrupted immediately. Discontinue cabozantinib unless the following criteria are met: 
• Subject is deriving clear clinical benefit as determined by the Investigator and agreed by the Sponsor• Toxicity can be managed with a dose reduction following recovery to Grade 1 (or baseline) and optimal medical care

AE: Adverse event.

^a Study treatment dose adjustment is only needed if the toxicity was deemed related to cabozantinib treatment or had an unclear relationship to cabozantinib treatment.

^b It is recommended that dose holds be as brief as possible.

Guidelines for the management of specific AEs are provided in Section 6.5.5.

5.1.3.5.3

Cabozantinib or M8891 Dose Reinstitution

If the subject recovers from his/ her toxicities to CTCAE version 4.03 Grade \leq 1 or to the baseline value (or lower) and the toxicity was unrelated to study treatment, then study treatment may be restarted with no change in dose.

If the subject recovers from his or her toxicities to Grade \leq 1 or to the baseline value (or lower) within 2 weeks and the AE was deemed possibly related to study treatment, then study treatment may be restarted at a reduced dose (see Section 5.1.3.5).

In case of dose reduction, re-escalation of cabozantinib or M8891 to the previous dose is not allowed.

5.1.4

Follow-up

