During the scheduled safety visits, subjects, in whom the calculated QTcF interval average increases to $>$ 500 ms or $>$ 60 ms change over baseline during treatment with M8891 combined with cabozantinib, must interrupt study treatment until further clinical evaluation. ECGs should be repeated if QTcF interval is outside the range until resolution (Table 12, Section 6.5.5). To assess the safety and tolerability of the study intervention, an ECG can be repeated at the Investigator's discretion at unscheduled visits. Start and end of resting time and ECG time will be recorded in the eCRF.

Abnormalities in the ECG that lead to a change in subject management (e.g., dose reduced or withheld, treatment discontinued, requirement for additional medication or monitoring as described in Table 12, Section 6.5.5) or result in clinical signs and symptoms are considered clinically significant for the purposes of this study and will be deemed adverse events. If values meet criteria defining them as serious, they must be reported as SAEs.

7.5

Pharmacokinetics

7.5.1

Part 1, M8891 Single Agent, Solid Tumors

For the PK analysis, the plasma level of M8891 will be analyzed by the analytical laboratory selected under responsibility of the Sponsor, using an appropriate validated bioanalytical method. Urine level of M8891 will be analyzed using an appropriate qualified method.

Full details of the bioanalytical method used will be described in a separate bioanalytical report. Plasma concentrations of M8891 and its metabolites will be analyzed as indicated in Table 1.

At each time point, 3 mL (2 aliquots of 1.5 mL) blood will be collected. The exact blood volume will be indicated in the Laboratory Manual. For all clinical and research studies, the total blood volume (mL) drawn in a 30-day period will never exceed the 280 mL.

Actual date and time of M8891 administration and PK actual sampling date and time will be recorded in the eCRF.

The PK sampling (and corresponding CCI sampling) schedule may be modified based upon emerging PK information collected during the study with the provision that the overall amount of blood to be collected for PK sampling is not increased.

List of PK parameters:

- C_{max} : Observed maximum plasma concentration
- t_{max} : Time to reach maximum observed plasma concentration
- $AUC_{0-\infty}$: Area under the concentration-time curve from time zero extrapolated to infinity, based on the predicted value for the concentration at t_{last}

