8.5 Description of Statistical Analyses

8.5.1 General Considerations

The following summary statistics will be used to summarize the trial data per Part and dose level unless otherwise specified:

- Continuous variables: number of not missing observations, mean, standard deviation, median, minimum, and maximum
- Categorical variables: frequencies and percentages.

All summary statistics will be described in detail in the respective Integrated Analysis Plan. There is no formal significance level for this trial and all analyses are considered descriptive.

The cutoff for the analysis will be as follows:

For the analysis after the end of Part 1, the cutoff will be Last Subject Last Visit (LSLV), or 4 months after the last subject enrolled into the monotherapy dose escalation cohort has finished their DLT period, whichever comes first.

For both dose escalation parts, the analysis will focus on the number of subjects experiencing a DLT. The SMC will receive results of a Bayesian two-parameter logistic model with overdose control updated with the observed DLT data for SMCs dedicated to dose escalation decisions ([Babb 1998; Neuenschwander 2008](#)). Recommendation is based on a loss function (probabilities of being in one of the four toxicity probability intervals will be multiplied with a loss term as follows:

$$0 * P(\text{target dosing (0.17-0.33)}) + 1 * P(\text{for over (0.33-0.67] or under dosing [0-0.17]}) + 2 * P(\text{excessive dosing (0.67-1]}).$$

Glossary:

(x.xx-y.yy] = lower limit excluded, upper limit included in the penalties
[x.xx-y.yy] = lower limit included, upper limit included in the penalties

In addition, only doses that have a corresponding probability of less than 25% that the true DLT rate is more than 33% (overdose control) are recommended by the model. The recommended dose level from the Bayesian model for the next cohort is the dose with the lowest loss function from all doses fulfilling the overdose control rule.

- MTD definition

The target DLT rate for the MTD definition is 30%. The MTD suggested by the model (if reached) will be defined as follows:

Highest tested dose with estimated DLT rate $\leq 30\%$. Additionally, the following needs to be fulfilled:

- The upper bound of the 95% credible interval of a potential MTD is not more than 40% and
- The estimated DLT probability for the suggested MTD is above or equal to 17%.

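### Cycle 1 of Part 2A has no single rule for reducing or interrupting cabozantinib, and the sentence a site follows can decide whether a subject without a DLT stays evaluable

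*Protocol*

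**What the plan says.** On reduction, Protocol Section 5.1.3.5.2 opens with a rule specific to the study part: "After completion of the DLT period in Part 2A and in all cycles of Part 2B, the dose of cabozantinib can be adjusted". The permitted steps, set out in Table 9, are 40 mg first and 20 mg second. The bullets below that opening rule are introduced as applying to modifications, which the lead-in defines as reductions or interruption. One of them states: "Doses may be modified at any time while on study". The bullet after that allows modification at toxicity grades lower than those in Table 10, again with no cycle limit. Section 5.1.3.2.1, which describes Part 2A itself, permits adjustment to 40 or 20 mg to manage adverse events and leaves cabozantinib reduction to the Investigator's judgement. Neither statement excepts Cycle 1.

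On interruption, Section 5.1.3.5.2 says: "Interruption of cabozantinib treatment for AEs may occur at any time (except from Cycle 1 in Part 2A) per Investigator discretion". Table 10 in the same section says for Grade 3: "Cabozantinib should be interrupted unless the toxicity can be easily managed with a dose reduction and optimal medical care", and for Grade 4: "Subjects should have cabozantinib interrupted immediately". Table 8, for M8891, is introduced as applying from Cycle 2 onwards. Table 10 carries no such limit. Section 7.4.5.2, repeated in footnote c of Table 4, says that subjects whose average QTcF exceeds 500 ms or rises by more than 60 ms "must interrupt study treatment until further clinical evaluation". Table 4 schedules ECGs on Day -1 and on Days 1, 8 and 15 of Cycle 1.

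On evaluability, Section 5.1.3.2.1 and Table 13 keep a Part 2A subject in the DLT analysis if at least 80% of the planned Cycle 1 dose of each drug was received, or if the subject had a DLT. Section 5.1.3.3 lists among the DLTs: "Any treatment interruption > 7 days or $> 30\%$ of total dose in Cycle 1 due to AEs", where the events are not due to the disease or to concomitant medication.

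**The concern.** A site with a Part 2A subject in Cycle 1 who has an adverse event attributed to cabozantinib can find text in the protocol for reducing and text against it. It can also find text for holding the drug and text that appears to bar a hold. That is a subject-safety problem first, because the instruction is needed quickly and should have one reading.

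It is also a measurement problem. Part 2A estimates the DLT rate of M8891 given with cabozantinib 60 mg. A reduction in Cycle 1 changes the regimen being observed. A reduction or hold can also take a subject without a DLT below 80% of planned cabozantinib, which removes that subject from the Bayesian model because of toxicity. Two sites facing the same event could each follow the protocol and produce different DLT data.

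**Working it through.** The plan gives no figure on this point to reproduce. It sets no error rate either: "There is no formal significance level for this trial and all analyses are considered descriptive". The check is dose arithmetic on the protocol's own limits.

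Inputs:
- Cabozantinib 60 mg daily, reduced to 40 mg at the first step (Table 9).
- Cycle 1 of Part 2A has 21 days of the combination, preceded by one day of M8891 alone (5.1.3.2.1).
- Evaluability limit: 80% of each drug (5.1.3.2.1, Table 13).
- Interruption DLT criterion: more than 7 days, or more than 30% of total dose (5.1.3.3).

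Assumptions: dosing is otherwise complete, no other DLT criterion is met, and the 30% limb is applied to cabozantinib alone.

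Planned cabozantinib is 21 × 60 = 1260 mg. The 80% limit is 1008 mg. A 30% loss is 378 mg.

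Reduction to 40 mg with first reduced dose on Day k: received = (k − 1) × 60 + (22 − k) × 40 mg.

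| First day at 40 mg | Received | Share | Loss | Status |
|---|---|---|---|---|
| Day 1 | 840 mg | 66.7% | 33.3% | below 80%; DLT status unclear |
| Day 3 | 880 mg | 69.8% | 30.2% | below 80%; DLT status unclear |
| Day 4 | 900 mg | 71.4% | 28.6% | excluded |
| Day 9 | 1000 mg | 79.4% | 20.6% | excluded |
| Day 10 | 1020 mg | 81.0% | 19.0% | evaluable |

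For a start on Days 1 to 3 the loss exceeds 30%, but the criterion speaks of an interruption, so the text does not say whether a reduction can meet it. If it can, the subject has a DLT and stays in the set. If not, the subject is excluded.

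Hold of h whole days: received share = (21 − h)/21.
- 4 days: 17/21 = 81.0%, evaluable.
- 5 days: 16/21 = 76.2%, excluded; loss 23.8%, not a DLT by this criterion.
- 6 days: 15/21 = 71.4%, excluded; loss 28.6%, not a DLT by this criterion.
- 7 days: 14/21 = 66.7%; loss 33.3%, a DLT by the 30% limb.

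If both drugs are held, M8891 (22 planned doses) shows the same gap: 17/22 = 77.3% after 5 missed days and 16/22 = 72.7% after 6.

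Effect on a cohort of 3 whose other two subjects have no DLT: the same subject contributes to 0/3 if dosing stays at or above 80%, to 0/2 if excluded, and to 1/3 if classed as a DLT. Section 5.1.3.2.1 replaces subjects only to reach 2 evaluable per cohort, and Section 8.5.3.2 updates the model with evaluable subjects only, so one exclusion can stand without replacement.

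**The case against.** The strongest reply is that the specific rule governs the general one. The opening paragraph of 5.1.3.5.2 names Part 2A and the DLT period, whereas the bullet on modifying doses at any time covers both Part 2A and Part 2B. The sentence before it in that bullet refers to unacceptable toxicity, which 5.1.3.2.1 defines for Part 2A as events meeting DLT criteria. A DLT in the DLT period already means stopping M8891 and leaving the study. This narrows the conflict without removing it. The protocol states no order of precedence, the next bullet extends modification to lower-grade toxicity, and 5.1.3.2.1 is itself specific to Part 2A yet has no Cycle 1 exception.

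On interruption the reply is stronger. A reader might infer that the protocol forbids holding cabozantinib in Cycle 1 even for a Grade 4 event or a long QTcF. The text does not go that far. The exception is attached to holds at the Investigator's discretion and can stand beside the mandatory QTcF hold, and Table 10 is headed as recommended guidance. What remains is that its Grade 3 and Grade 4 entries conflict on their face with the exception, and nothing says whether they, or the QTcF hold, are outside it. A reader might also see the DLT list as contradicting the exception. It does not: it classifies interruptions that occur, without permitting them, and it also serves Part 1.

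Nor is the handling of under-dosed subjects missing. The 80% rule, the retention of subjects with a DLT and the replacement rule are all stated. The SMC can also class a clinically significant event as a DLT. The one gap is whether a reduction can meet the criterion written for interruptions.

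**Conclusion.** The point holds as an internal inconsistency that should be corrected. Cycle 1 of Part 2A has conflicting text on reduction, and an exception for interruption whose reach is not stated. The SAP covers only the monotherapy escalation and does not resolve either.

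Under the dosing assumptions above, a subject without a DLT is excluded after a step to 40 mg starting on Days 4 to 9, or after a 5- or 6-day hold. Starts on Days 1 to 3 are ambiguous. The Day 1 figure of 66.7% should therefore not be read as plain exclusion.

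Three limits apply. First, the effect concerns only events that are not DLTs themselves, such as intolerable Grade 2 toxicity, Grade 3 events on the DLT exclusion list, or Grade 3 neutropenia without fever. Many Grade 3 and 4 non-hematologic events are DLTs in any case and keep the subject in the set. Second, one exclusion is a third of one cohort. A reader might take this as a third of the evidence, but the model accumulates cohorts, is set up using Part 1 data, and 6 to 15 subjects are planned, so one subject is 1/15 = 6.7% to 1/6 = 16.7% of Part 2A. Third, a reader might infer a bias of known direction. The exclusions are related to toxicity, but 0/2 is neutral between the 0/3 and 1/3 that could have been recorded only in the sense that it carries neither answer. The direction depends on how the subject would otherwise have been classed. The documents give no frequency for such events.

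**What to change.** Reconcile Section 5.1.3.5.2 with Section 5.1.3.2.1, Table 10 and Section 7.4.5.2 (with the matching Table 4 footnote), so that Cycle 1 of Part 2A has one rule for cabozantinib reduction and one for interruption. The interruption rule should say whether the Table 10 holds and the mandatory QTcF hold fall outside the Cycle 1 exception. What those rules contain is a clinical decision for the sponsor.

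In Section 5.1.3.3, state whether a dose reduction in Cycle 1 counts towards the criterion of more than 30% of total dose, and whether that share is taken per drug. The 80% rule can then be applied as written.

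The cost is a protocol clarification. It needs no change to the sample size, the model or the assessment schedule.

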5.2.1.2 Part 2, M8891 combined with Cabozantinib, mRCC

5.2.1.2.1 Part 2A, Dose Escalation

In Part 2A, M8891 will be combined with cabozantinib for subjects with mRCC who have progressed to 1 or more previous lines of therapy for metastatic disease. The starting dose of M8891 will be 20 mg QD (See Section 5.1.3.2.1). Three pre-specified dose levels of M8891 are planned (20 mg, 35 mg and 60 mg) although the SMC may add or skip a dose, as long as it does not exceed the dose level of M8891 that has already been declared to be safe in Part 1 (See Section 5.1.3.2.1).

Similar to Part 1, a Bayesian two-parameter logistic regression model with overdose control will be used to assist the SMC with dose selection for the next cohort and to determine the MTD/RDE of M8891 combined with cabozantinib 60 mg QD for Part 2B. For the implemented overdose control, overdose is defined as a DLT rate of > 33%. For each dose level the risk of overdose will be calculated, and only dose levels for which this risk is lower than 25% will be recommended by the model. The decision on the next dose is made by the SMC.

In Part 2A, cabozantinib will be used at the approved 60 mg FBE daily dosage with dosage adjustments to 40 or 20 mg permitted to manage AEs (Section 5.1.3.5). The cabozantinib tablet formulation (CabometyxTM) is approved in USA and in the European Union (EU) at a 60 mg FBE daily dosage for the treatment of patients with advanced RCC. While simulations showed that the

20, 40, and 60 mg cabozantinib starting dosages were all predicted to reduce tumor growth, the 60 mg dose resulted in the greatest reduction in tumor growth, best objective response rate (ORR), and lowest rate of disease progression. In the review of the New Drug Application for cabozantinib for the treatment of patients with RCC, FDA addressed the issue regarding the appropriateness of dose selection given the high percentage of dose reductions in the METEOR study (A Study of Cabozantinib vs Everolimus in Subjects with Metastatic Renal Cell Carcinoma). Based on their review, FDA concluded that: (1) most adverse reactions were successfully managed with dose interruptions and supportive measures; (2) Exposure-Response modeling indicated that lower starting doses could possibly compromise activity of the drug with decreased response rates; and (3) the dose selection of 60 mg daily was adequate based on Exposure-Response analyses and a safety profile that is acceptable for the patient population (Lacy 2018).

5.2.1.2.2 Part 2B, Dose Expansion

Following Part 2A, the safety and tolerability of M8891 combined with cabozantinib will be investigated in an expansion cohort of 30 evaluable for response subjects with mRCC, for assessment of early clinical activity with an interim analysis after 15 subjects. The dose of M8891 in Part 2B will be determined by Part 2A and cabozantinib will be given at 60 mg QD (See Section 5.1.3.2.1).

